Protocol Title: Text BP: Comparing standard office based follow up versus text-based remote monitoring in the management of postpartum hypertension.

NCT number: 03185455

Date of Document: 11/9/2016

Protocol title: TextBP: Comparing standard office based follow up versus text-based remote monitoring in the management of postpartum hypertension

Short title: Remote surveillance of postpartum hypertension

Brief description of protocol:

Women with hypertensive disorders of pregnancy need postpartum blood pressure (BP) surveillance to detect persistent hypertension. Various barriers result in only 30% attendance at postpartum BP visits. A more effective strategy is needed. Women with hypertension of pregnancy will be randomized to either text-based monitoring or office visits. Those randomized to the intervention will receive a BP cuff and text in their BP to an automated, clinician derived, HIPAA compliant text-based algorithm.

Abstract:

Hypertension is a leading cause of maternal morbidity, mortality and obstetrical readmissions. Peak blood pressure usually occurs 3-6 days postpartum, and is typically unaccompanied by warning symptoms. Although there is a clear need for effective and reliable blood pressure surveillance after delivery, there are significant obstacles to in-person visits in the immediate postpartum period, including sleep deprivation, newborn care, and transportation needs. These barriers have proven real as we observed only 30-50% attendance to office blood pressure visits following delivery. This proposal will investigate whether text-based communication between patients and providers is an effective alternative method for monitoring postpartum hypertension in at risk women.

Women with hypertensive disorders of pregnancy with access to a cell phone with unlimited text message capabilities will be randomized to either office visit blood pressure checks after discharge or receive a blood pressure cuff and text in blood pressures for two weeks postpartum using a standardized, HIPAA compliant, physician derived automated platform.

Objectives

Overall objectives:

The objective of this study is to compare office based blood pressure visits (standard of care) to remote surveillance using a text-messaging system for monitoring postpartum hypertension. The goal of this study is to determine if text messaging is an effective, patient centered way to monitor blood pressure in the postpartum period. By supporting patient self-care and using health information technology, we hope to adopt a method that can achieve best outcomes in our current patient, largely underserved minority population.

Primary outcome variables:

The primary outcome is the percentage of patients in which a single blood pressure is obtained in the first 10 days following discharge. Within the texting group, the percentage of patients in whom blood pressure values are obtained at 72 hours and 7-10 days postpartum, in accordance with ACOG recommendations, will be assessed as well.

Secondary outcome variables:

Secondary outcomes will include ability of providers to initiate antihypertensive medication, number of postpartum emergency room visits for hypertension and readmissions for persistent postpartum hypertension, patient satisfaction with blood pressure surveillance, and future health awareness/patient engagement by assessing number of patients with a primary care/cardiology appointment scheduled by two weeks postpartum. Additionally, cost data will be compared between the two arms.

Background:

Hypertensive disease is a leading cause of maternal morbidity and mortality and obstetrical readmissions in the US, accounting for 27% of the obstetric readmissions in 2009. The majority of patients readmitted with hypertension are diagnosed with a hypertensive disorder of pregnancy on initial admission for delivery, indicating that these readmissions result from disease progression in contrast to new onset disease, and are plausibly preventable. Given the risk of strokes and seizures from persistent or worsening disease, early recognition of progression and aggressive treatment is critical in the postpartum period. For these reasons, identifying patients who are at risk for persistent disease and being proactive in their postpartum care can decrease maternal morbidity.

Current evidence suggests that delayed mobilization of interstitial and extravascular fluid into the intravascular space predisposes women with preeclampsia to sustained hypertension, explaining the increase in blood pressure 3-6 days postpartum. This peak blood pressure postpartum usually occurs after obstetric discharge. Therefore, identification of patients at the optimal time, early enough that intervention can prevent readmission and maternal morbidity and mortality but not too early where intervention may be unnecessary, is critical. As such, the recent ACOG Hypertension in Pregnancy guidelines recommend monitoring blood pressure at 72 hours postpartum and again in 7 to 10 days in women diagnosed with a hypertensive disease of pregnancy. However, there are no recommendations on how to accomplish this.

Currently, all patients with known hypertension or a diagnosis of hypertensive disorder of pregnancy receive 1:1 nursing education about preeclampsia using an approved patient education sheet prior to discharge. Anti-hypertensive agents are initiated as needed based on a standard blood pressure based algorithm. All patients are then instructed to follow up in the office where they received prenatal care 4-6 days postpartum for a blood pressure visit. Given the difference in average length of stay, this equates to post discharge days 3-5 for patients who underwent vaginal delivery and days 2-4 for patients who underwent a cesarean delivery.

While surveillance during this time period is critical, a standard visit based approach has not proven effective in this population of newly delivered women. There are significant obstacles to in-person visits in the immediate postpartum period, including sleep deprivation, care of a newborn, difficulty with transportation, and discomforts due to post-delivery recovery. These barriers have proven real as we observed only 30-50% attendance to in-person, office based blood pressure visits scheduled immediately postpartum over the last 2 years. Utilizing text messaging for surveillance plausibly addresses some of the barriers unique to this population.

Given the significant morbidity and mortality attributable to preeclampsia and persistent and progressive postpartum disease coupled with 1) the observation that postpartum hypertension is the leading cause of obstetrical readmissions (over 45% of all readmissions within 7 days in Fiscal Year 14) and 2) our current surveillance is inadequate and generally reaches fewer than half of all women at risk, we sought to test an innovative approach to surveillance using sms-text messaging as an alternative to in-person follow up.

With support and partnership through the Penn Medicine Center for Health Care Innovation, we previously performed a small pilot study of 32 women with hypertensive disorders of pregnancy. The goal of this initial pilot was to determine if we could engage patients in remote postpartum hypertension surveillance and obtain important and necessary preparatory patient feedback to develop this proposal. Patients were provided with a home blood pressure cuff and were instructed on its use.

They were asked to send in blood pressures on the seven days following discharge from the hospital after their delivery. We found that 84% of the patients engaged in the study and texted at least one blood pressure in the 7 days and nearly 65% of patients sent in blood pressures on 5 of the 7 days requested. Of the 32 patients in the pilot, only six (19%) returned for their scheduled office blood pressure check (routine care). Patients reported that text messaging was an active way for them to participate in their care and increased their awareness of postpartum hypertension.

While we found remote surveillance of blood pressure with mobile phone texting to be a feasible, convenient, affordable, and patient-centered way for patients and providers to monitor blood pressure in the postpartum period, further testing is needed prior to widespread adoption. We have since developed a bidirectional, HIPAA compliant, clinician derived, automated text based hypertension algorithm that provides reminders to patients to text in blood pressures, timely automated responses to patient texts based on a preset clinical blood pressure algorithm, and alerts clinicians to preset high blood pressure values that require response. We have already tested this with seven patients and received feedback ensuring its functionality.

Using this two-way text based clinician derived automated hypertension algorithm, we will perform a randomized controlled trial comparing the effectiveness of these two strategies usual visit based care to this text based innovative strategy. Our overall goal is to improve postpartum blood pressure monitoring in women with a previously diagnosed hypertensive disorder of pregnancy. If, in fact, text message surveillance decreases maternal morbidity and readmissions, this would have large implications for patient care and enhance the way we perform postpartum blood pressure monitoring. Additionally, this has potential generalizability to other populations that require frequent blood pressure monitoring (adult cardiovascular, heart failure, etc.) as well as possible use in monitoring other postpartum conditions (depression, breastfeeding).

Study design

Design:

The study will be an un-blinded randomized, two arm trial. Patient will be randomized to usual one time office visit based blood pressure check or to text-message based remote surveillance for two weeks. Randomization will be performed using a computer generated sequence using REDCAP. Demographic information will be collected from those who decline randomization or are ineligible in order to assess patient characteristics of those willing to be randomized and who meet eligibility.

Study duration:

Estimated length of time is 12 months. We believe it will take no more than 9 months to enroll all of the patients and allow three months for data analysis. This is based on our previous ability to enroll patients in a pilot study investigating remote surveillance. The subjects will participate in the study for two weeks (14 days) following discharge if they are randomized to the text-message arm.

Resources necessary for human research protections:

The research staff will include Maternal Fetal Medicine fellows and attendings and the Maternal and Child Health Research inpatient clinical research team. We have a Maternal and Child Health Research program in our OBGYN department with an established track record of successful recruitment in the antepartum, intrapartum, and postpartum periods. Patients will be recruited by Maternal Fetal Medicine fellows (primarily [name]), with assistance from the postpartum nursing leadership and inpatient clinical research coordinators within MCHRP. Recruitment for the pilot mentioned above occurred with assistance from the womens health postpartum nursing leadership. The research

coordinators will enroll into the WaytoHealth Texting Platform. Data collection will be performed by [name].

The population will be approached on the postpartum recovery floor prior to discharge. The blood pressure cuffs will be stored on the postpartum unit and patients will be instructed on use if they are randomized to the text-message arm.

A Maternal Fetal Medicine nurse, with assistance from [name], will respond to elevated blood pressures that are sent in the text message arm and clinical staff at the practices will check office blood pressures as currently designed for those in the standard of care arm. All research staff and those involved in responding to blood pressures will receive education regarding the protocol and their duties prior to the start of the study.

Target population:

Postpartum women with a diagnosis of chronic hypertension, gestational hypertension, or preeclampsia will be eligible for the study.

Subjects enrolled by Penn Researchers:

206

Accrual:

This study will take place at the Hospital of the University of Pennsylvania (HUP). We perform approximately 4200 deliveries annually. Our patient population is primarily from the surrounding urban region. The majority receives prenatal care at our institution and 10% are unregistered at our hospital. Based on fiscal year 2014 at HUP, 68% of patients were African American, and 10% of patients had preeclampsia and would be potentially eligible. Therefore, about 420 women annually have a hypertensive disorder and would be eligible for this proposed study.

Our sample size calculation is based on the show rate for office blood pressure visits since initiation of this standard of care and the results from our pilot study. The range of show rates in these office visits is 30-50% and our preliminary data suggests that approximately 80% of patients text at least one blood pressure in the 7 days post discharge. Using a more conservative usual care show rate of 50%, with an alpha of 0.05, 80% power and using a 2-sided t-test, we would require 103 patients in each arm to detect this 1.4 fold increase blood pressure ascertainment.

Key inclusion criteria:

Women with chronic hypertension, gestational hypertension, or preeclampsia who deliver at HUP will be eligible. All patients must be 18 years old, able to speak and read English, have a hypertension diagnosis listed above, and have access to a cell phone with unlimited text message capabilities.

Key exclusion criteria:

Women without access to a cell phone with unlimited text message capabilities will be excluded from the study in order to eliminate barriers to participate in remote surveillance. However, we will track the number of women not eligible for this reason in order to understand generalizability in an urban population. Women who cannot read or speak English or are younger than 18 years of age will be ineligible.

Populations vulnerable to undue influence or coercion:

Patients will specifically be told what arm they are in following randomization. Those not randomized to text-messaging and those electing not to participate will receive the current standard of care (office based visit).

Subject recruitment:

Eligibility will be determined in the postpartum period on the postpartum recovery unit by the research team which will include the Maternal Fetal Medicine fellows, the MCHRP inpatient clinical research coordinator team, and postpartum nursing leadership (see eligibility algorithm). Women will be approached at time of their routine hypertension education, prior to discharge, by the research coordinators. Enrollment in the study will take place at this time if they agree, and entry into the automated platform will occur prior to discharge for those randomized to this arm. Those randomized to usual care will receive their office visit date/time prior to discharge.

Subject compensation:

None

Procedures:

The study will be performed as a pilot randomized control trial. Patients will be randomized to either having routine office based blood pressure check visit or to remote text-message based surveillance using a previously developed automated algorithm (WaytoHealth). Study flow chart is attached.

Postpartum patients with a hypertensive disorder of pregnancy will be approached for enrollment by trained study personnel on the recovery unit. Participants will be randomized 1:1 using a computer generated random number table of permuted blocks. Recruitment will occur prior to discharge at time of hypertension education and randomization will occur once consent is obtained.

Those randomized to the standard protocol for blood pressure monitoring will be scheduled for an office based nursing blood pressure visits 4-6 days postpartum. The date and time of the office appointment is specified in the discharge document and reviewed with the patient prior to discharge. Care at this visit is based on a physician derived algorithm. Women randomized to the text-based surveillance arm will be given an automatic Omron® blood pressure cuff and instructed on its use by research team members prior to discharge. Patients will be enrolled into the texting program platform developed through Way to Health. A starting introductory text message is sent by the Way to Health platform to the phone number provided on day of discharge. Patients receive reminders to text message their blood pressures twice daily for two weeks postpartum, starting on the day after discharge. Immediate feedback is provided to the patient based on a preprogrammed automated algorithm. The primary investigator is alerted with pre-specified severe range blood pressure values (systolic blood pressure > 160 mmHg or diastolic > 100 mmHg) via text message or email and care is escalated as needed based on the same outpatient algorithm used in the office. All patients will receive a phone call 3 weeks after delivery for a patient satisfaction survey. All patients will be instructed to return for their usual postpartum visit at 4-6 weeks.

Analysis plan:

Chi square or Fishers exact test will be used to compare categorical data. T-test will be used to compare parametric data. Mann-Whitney U test will be used to compare non-parametric data. Univariate comparisons will be made between exposure and outcome. Multivariable logistic regression models will be created to control for potential confounders. Outcomes will be analyzed by the intention to treat principle.

Subject confidentiality:

Participant's private information will be viewed by study personnel only. All information collected as part of the research study will be placed into a database which will be kept on a password protected computer which can be accessed by the PI and key personnel only. Each study subject will be assigned a study number.

The consent form will include statements informing subjects that privacy of information sent through text messaging cannot be guaranteed and that only blood pressure values should be sent to the platform. Only the minimum information necessary is placed in the text messages to reduce the chance of anyone seeing details about the patient and their health. Patients will be encouraged to put a screen lock on their device.

Subject privacy:

All recruitment, informed consent, and conversations related to study participation will be performed in private work spaces. Patient randomized to the text message arm will sign a waiver stating that privacy of information sent through text messaging cannot be guaranteed and that only blood pressure values should be sent to the platform. Only the minimum information necessary is placed in the text messages to reduce the chance of anyone seeing details about the patient and their health. Patients will be encouraged to put a screen lock on their device.

Consent process

Overview:

Consent will be obtained by the study investigators or assigned research staff when receiving postpartum hypertension education prior to discharge. The study will be explained in lay person terms to each eligible woman by one of the investigators or assigned research staff. The consent form will be given to the patient and she will have ample time to read the consent form on her own. The woman will be asked if she has any questions regarding the study protocol or the consent form. All questions will be answered. The woman will be informed that her care will not be affected if she chooses not to participate in the study and that she may discontinue participation at any time point. She will be made aware of what is needed in the intervention arm including taking her blood pressure and texting the result either once or twice daily for seven days after discharge from the hospital. She will be told a text message will be sent every morning saying "Good morning. Please send us a morning blood pressure reading." and that she will receive a text message back based on the value of her reading. Women will be informed that while the platform is HIPAA compliant, text messaging is not a completely secure means of communication.

Potential study risks:

There is a risk of loss of confidentiality in patients randomized to the intervention arm as texting technology was not built for secure communications. Therefore, privacy of information sent through text messaging cannot be completely guaranteed. However, as texting has the potential to be a more patient-centered, effective means of remote surveillance, we believe the potential benefits outweigh the risks. Additionally, patients will only be texting blood pressure readings and responses in the text messages have minimum information necessary to reduce the chance of someone else seeing any details about their health. The platform includes only the patient's name and cell phone number, each matched to a study ID number. The privacy policy of WaytoHealth ensures that no information shared with the site will be sold or distributed and the site is password protected. Patients will be encouraged to have a security lock on their phones. As only those with unlimited texting services will be included in the study, there is no additional financial cost to receiving or sending text messages.

Potential study benefits:

Potential benefits include improved patients centered means of monitoring blood pressure in the postpartum period. It is unclear whether remote surveillance with text messaging improves blood pressure ascertainment and can reduce morbidity so both arms have the potential benefit of being in the more effective treatment arm.

Alternatives to participation:

Alternatives to participation involves having office based blood pressure checks per usual practice.

Data and safety monitoring: PI

Risk/benefit assessment: There is minimal risk to participation in this study. Women may directly benefit from participation in the study related to improved blood pressure surveillance in the immediate postpartum period.

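### Does capturing office and texted readings by different routes tilt the primary outcome toward texting enough to require a change?

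*Combined protocol and SAP*

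**What the plan says.** Under Primary outcome variables, the endpoint is "the percentage of patients in which a single blood pressure is obtained in the first 10 days following discharge". Neither the setting nor the source of a qualifying reading is given.

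The routes differ by arm:

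- **Text arm.** Procedures has women prompted twice a day to text readings to the Way to Health platform.
- **Office arm.** Resources necessary for human research protections says that "clinical staff at the practices will check office blood pressures as currently designed for those in the standard of care arm". Background describes current practice: "All patients are then instructed to follow up in the office where they received prenatal care 4-6 days postpartum for a blood pressure visit". Accrual adds that "The majority receives prenatal care at our institution and 10% are unregistered at our hospital", so some of those offices may be elsewhere.

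Study design states that "The study will be an un-blinded randomized, two arm trial". Data collection is assigned to a member of the team, but no record source is named. Analysis plan covers tests, regression and intention to treat only. Procedures includes a call to every participant three weeks after delivery, for satisfaction. The flow chart mentioned there is not in the available copy.

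Three statements bear on whether office attendance can be captured. Background gives a show rate of 30-50% observed over two years. It also says of the 32 pilot women that "only six (19%) returned for their scheduled office blood pressure check (routine care". Subject recruitment says "Those randomized to usual care will receive their office visit date/time prior to discharge".

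**The concern.** When the endpoint is whether a reading was obtained, failure to find a reading is not missing data: it counts as a failure. One arm's readings arrive unaided and the other's must be retrieved. A woman in the office arm who attends an outside practice could be scored as having no reading, while a woman in the text arm is exposed to that error only if she never texts. The more plausible direction of error therefore favours texting. In an unblinded trial it would not be visible in the reported percentages.

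At stake are the size of the effect, which would inform adoption of texting, and, if the arms were truly equal, the false-positive rate. A common check built on the planned three-week call, backed by records and counting any route in both arms, looks like a cheap correction.

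**Working it through.** **The plan's own figure.** Inputs from Accrual: office show rate 50%, a 1.4-fold increase (1.4 × 50% = 70%), two-sided alpha 0.05, power 80%. The two-proportion formula gives 93 per arm without continuity correction and 103 with it, which matches the protocol. Both planning rates are by assigned route: office attendance on one side, and on the other a pilot figure in which "approximately 80% of patients text at least one blood pressure in the 7 days post discharge".

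**Assumptions needed to size the problem.** The documents give no rate of missed readings.

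- Outside care: 10%. This borrows the unregistered share, which is not a rate of prenatal care elsewhere.
- All outside visits unseen.
- Non-texters who attend an office: 6/32 = 18.75%. This is the pilot rate among all 32 women, not among non-texters.

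**Case A: office readings already count in both arms.**

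- True office rate 50.0%; recorded 50 × 0.9 = 45.0%.
- True text rate 70 + 30 × 0.1875 = 75.6%; recorded 70 + 30 × 0.1875 × 0.9 = 75.1%.
- True difference 25.6 points; recorded 30.1 points; inflation 4.4 points (from unrounded values).
- Range: 5.0 points if no non-texter attends an office, 3.5 if half do, 2.2 if only half of outside visits are unseen, 8.9 if outside care is 20%.

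**Case B: each arm is counted by its assigned route, as in the sample-size rates.**

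- Recorded without the common check: 70 − 45.0 = 25.0 points.
- With complete office retrieval and texts alone in the text arm: 70 − 50 = 20.0 points.
- With the common any-route check: 75.6 − 50.0 = 25.6 points.

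In Case B the any-route check adds 5.0 points to the office arm and 5.6 to the text arm, so the gap does not shrink. It shrinks only if text-arm office readings were already going to be counted (Case A), or if retrieval is improved without changing what counts in the text arm. The protocol does not say which case applies.

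**Two weak inputs.** The pilot's 19% comes from women who also had a scheduled office visit. In the trial, Procedures describes that visit only for the office arm, so the rate among non-texters could be much lower. The 50% is itself the upper end of an observed show-rate range. If outside visits went unseen when it was measured, 50% is the recorded rate and the true rate would be 50/0.9 = 55.6%.

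**Effect on the conclusion.** The 95% half-width is 1.96 × √((0.25 + 0.21)/103) = 13.1 points. A 20-point difference clears this with or without a further 5 points.

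For equal true rates of 50%, solve t + (1 − t) × 0.1875 = 0.50, which gives t = 0.3125/0.8125 = 38.5% texting. Recorded rates are then 45.0% in the office arm and 50 − 61.5 × 0.1875 × 0.1 = 48.8% in the text arm. Exact two-sided rejection with 103 per arm rises from 4.6% to 8.2% (3.3% to 6.3% with continuity correction). With half of outside visits unseen it is 5.5% (4.0% corrected). In the pilot 84% texted at least once, so this null is a limiting case.

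**The case for a change.** The strongest opposing case has four parts.

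1. Scheduling a visit does not record attendance, and the protocol does not say how pilot attendance was verified or whether outside practices were covered.
2. The outcome is not restricted to the assigned route, so the intended rule is open.
3. The false-positive risk could be larger than shown above. If 10-20% of office readings were missed and none in the text arm, with equal true rates of 50-70%, the chance of a significant result for texting would be about 11-55% (8-49% continuity-corrected) instead of 2.5%.
4. Permission to obtain outside records and timely recall are hard to recover after the fact.

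The first two stand as descriptions of what is unwritten. The third stands as arithmetic, but its miss rates have no source in the documents, it allows no loss among texters, and it needs arms that are truly equal. The fourth has some force for record permission and less for recall. Postpartum days 4-6 equate to post-discharge days 3-5 or 2-4, so discharge is about day 1 or 2 and the 10-day window closes about day 11 or 12. A call at day 21 is then 9-10 days late. Answers would come from women who know their arm, and some would not answer.

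There is also a point in the other direction. A woman in the text arm may use the supplied cuff and not text the result. A rule admitting only texts and office readings would leave her a failure, so that rule is not neutral either.

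**Conclusion.** The concern does not require a change to the plan. It is correct that the routes differ and that the available text names neither the qualifying readings nor the place where office readings are sought. That is missing detail. The team has measured office attendance over two years and in its pilot, visits are booked before discharge, and data collection is assigned, so reviewing practice records is the natural way to fill the gap. Nothing in the protocol indicates that outside readings would be ignored.

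The size is conditional throughout. At an assumed 10% unseen, the office arm loses 5.0 points and the estimate is inflated by 3.5 to 5.0 points, depending on how many non-texters attend an office. Across the assumed loss rates tried, the inflation runs from 2.2 to 8.9 points. The planned 20-point effect remains significant in each case.

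Any-route counting is an estimand choice and not a clear correction. On the by-route reading that matches the sample-size rates, it takes the gap from 25.0 to 25.6 points. Part of the difference in routes is also the intervention itself: if the intended outcome is a reading that reached the provider by the assigned route, the contrast is what the trial sets out to measure.

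### Emergency visits and readmissions count only when attributed to hypertension, in an un-blinded trial with very unequal measurement; all-cause counts and the route of each visit should be reported beside them

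*Combined protocol and SAP*

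**What the plan says.** The Secondary outcome variables section lists the "number of postpartum emergency room visits for hypertension and readmissions for persistent postpartum hypertension". Both components are restricted by cause. The protocol does not say what makes a visit hypertensive, who decides, whether that person knows the arm, where the events are found, or over what period. It plans no all-cause count.

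Under Study design, "The study will be an un-blinded randomized, two arm trial", and "Patient will be randomized to usual one time office visit based blood pressure check or to text-message based remote surveillance for two weeks". Under Procedures, "Patients receive reminders to text message their blood pressures twice daily for two weeks postpartum, starting on the day after discharge". Study duration also gives 14 days after discharge for the text arm. The Consent process overview differs: women are told of "texting the result either once or twice daily for seven days after discharge from the hospital".

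Also under Procedures, severe-range texted values alert the investigator, and care is escalated as needed on the algorithm that the office uses. Data and safety monitoring is assigned to the PI. The Analysis plan names generic tests and intention to treat, and does not discuss unequal ascertainment.

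The Background ends with a conditional statement of purpose: "If, in fact, text message surveillance decreases maternal morbidity and readmissions, this would have large implications for patient care".

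**The concern.** A cause-specific event count compares fairly between arms if a given event has the same chance of being found, and of being given the qualifying label, in each arm. Two features of this design could break that condition.

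- **Labelling.** The arm is not masked, and one arm has a series of home readings that the other lacks. If those readings or the arm are known when a visit is classified, the same visit could be called hypertensive more often in one arm.
- **Detection.** The Abstract says that the postpartum peak usually comes without warning symptoms. A high value that is texted can start a chain of care. The same value in a woman who misses her office visit may never be seen.

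The effect could go either way. More readings may bring more hypertension visits, or may lead to outpatient treatment that prevents them. At stake is the reading of the outcomes closest to the morbidity statement in the Background. From the planned count alone, a reader could not separate a change in disease from a change in how often it was found or named.

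**Working it through.** **1. The plan's own figure.** The documents give no rate or sample size for these events. The one sample size is 103 per arm for the primary outcome (Accrual), at a usual-care rate of 50%, a 1.4-fold increase (70%), two-sided alpha 0.05 and 80% power.

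- Two proportions, uncorrected: n = [1.960 × √(2 × 0.6 × 0.4) + 0.842 × √(0.5 × 0.5 + 0.7 × 0.3)]² / 0.2² = 93.
- With continuity correction: (93/4) × [1 + √(1 + 4/(93 × 0.2))]² = 102.8, so 103.

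The stated figure reproduces, and nothing below changes it.

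**2. Readings requested.**

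| Source | Text arm | Office arm |
|---|---|---|
| Procedures, Study duration | 2 × 14 = 28 | 1 |
| Consent process overview | 1 × 7 to 2 × 7 = 7 to 14 | 1 |

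At the 30-50% attendance given under Accrual, the office arm yields 0.3 to 0.5 readings per woman. In the pilot, 84% of women texted at least one reading, and nearly 65% texted on 5 of the 7 days. So 28 is a ceiling, but the imbalance remains under either wording.

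**3. Labelling alone (all rates assumed).** Let the true all-cause event rate be 10% in both arms, with 40% of events labelled hypertensive in the office arm and 60% in the text arm.

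- Office: 0.10 × 0.40 = 4%, or 4.1 of 103 women.
- Text: 0.10 × 0.60 = 6%, or 6.2 of 103 women.
- Ratio: 6/4 = 1.5, with no difference in events.

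Exact binomial enumeration at 103 per arm gives the chance of a significant result: 9% with an uncorrected chi-square test and 5% with Fisher's exact test. The Analysis plan allows both tests. At these rates the distortion lies mainly in the estimate.

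The range, with the chi-square test and equal true rates of 5% to 20%:

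| Share labelled, office v text | Ratio | Chance of a significant result |
|---|---|---|
| 50% v 70% | 1.40 | 6% to 14.5% |
| 50% v 90% | 1.80 | 10% to 39% |
| 90% v 50% | 0.56 | 10% to 39% |

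Counting all-cause events in the same settings returns the chance to 4.4-5.2%.

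**4. Alerts, which are not visits.** If each reading has an assumed probability p of exceeding the alert level, independently, the chance of at least one alert in 28 readings is 1 − (1 − p)²⁸.

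- For p = 0.5%, 1% and 2%, this gives 13.1%, 24.5% and 43.2%.
- One office visit at 50% attendance gives 0.25%, 0.5% and 1%.

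For any given p, the text-arm figures are upper bounds. They assume all 28 readings are sent and that readings within a woman are independent.

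- With 7 to 14 readings, the range is 3% to 25%.
- With 28 readings and an assumed within-woman correlation of 0.2 (beta-binomial), it is 4% to 16%.
- With a correlation of 0.5, it is 2% to 8%.

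The documents give no probability that an alert leads to a visit, so none of this estimates the outcome.

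**The case against.** The strongest reply has four parts.

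**Biased attribution is not documented.** This stands. A reader might infer that visits are classified by people who know the arm and can see the texted readings. The protocol names neither the classifier nor any feed of texted values into the hospital chart. It says only that the platform is password protected and that alerts go to the investigator. The un-blinded design makes bias possible and does not establish it. For the same reason, it goes too far to call the count non-comparable between arms.

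**Both arms use the same escalation algorithm.** This stands for the rule. It does not equalise how often the rule is triggered.

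**Alert-driven visits are a consequence of the randomised strategy.** This stands. Counting them by intention to treat is legitimate in a comparison of two surveillance strategies, and an all-cause count would still include them. Only an interpretation of the count as morbidity needs more.

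**The morbidity claim is modest.** This largely stands. The Background sentence is conditional, the stated goal is better monitoring, and the benefits section calls a reduction in morbidity unclear. The Procedures call the trial a pilot, and the outcome is one of several secondaries. That limits the weight of the point but does not supply the missing definition.

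**Conclusion.** The point holds as a possibility that the plan leaves open: differential labelling and detection could shift the hypertension-attributed count, up or down, without a change in morbidity. The documents do not show that it occurs or in which direction.

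The 4% v 6% example rests entirely on assumed rates. The 13% to 43% figures bound the chance of an alert under their assumptions; reading them as a rate of excess visits would be wrong.

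The primary outcome and the 103 per arm are unaffected. Label: cheap improvement.

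**What to change.** - Keep the hypertension-attributed outcome. Add all-cause emergency visits and all-cause readmissions by arm, from the same source and over the same fixed window in both arms.
- Record how each hypertension visit arose (text alert, office visit or self-presented) and report the visits by route, descriptively.
- State in the Analysis plan that a difference in the hypertension-attributed count will not be read as a change in morbidity unless the all-cause count is consistent with it.
- Reconcile the Procedures and Study duration with the Consent process overview on how many readings are requested and for how long.

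The all-cause count removes only the attribution component. Alert-driven visits remain in it as part of the strategy's effect, and the route field describes them.

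The cost is a modest amount of extra data collection: every visit has to be captured, plus one field per hypertension visit. All-cause counts are also noisier because they include unrelated postpartum visits. They should therefore stand beside the cause-specific count and not replace it.
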